The immunogenicity of oral poliovirus vaccine (OPV) is lower in infants in developing countries than in infants in industrialised countries. The most widely used formulation of trivalent OPV is based on the 10:1:3 combination of vaccine types 1, 2, and 3 respectively. In the review by Patriarca et al. (1991), the median seroconversion rates of infants residing in developing countries for each virus strain following administration of three doses of OPV were:

- Poliovirus type 1 : 72%
- Poliovirus type 2 : 95%
- Poliovirus types 3 : 65%

A variety of factors have been proposed to explain the differences in response rates of infants between industrialised and developing countries.^{29,30}

One approach to improving the seroconversion rates to OPV in developing countries has been to provide infants and children with additional vaccine doses; for example another OPV dose may be administered at 9 months of ages, and a further dose in the second year of life ^{31,32,33,34} . However, routinely scheduled individual immunisation visits may not be practical in some settings in developing countries in older children. As a result, some countries have introduced mass immunisation campaigns for these subsequent OPV doses. While ensuring a higher rate of vaccine coverage, some evidence exists for vaccine administered in such campaigns to evoke better immune responses and higher seroconversion rates ^{35,36} .

Purpose of study

At the present time, no data exist on the effect if any on the immune responses to the components of OPV and CAIV-T when co-administered. In clinical trials to date, no other live virus vaccine has been administered within 1 month of a dose of CAIV-T. However, in many settings where children might benefit from an effective live influenza vaccine such as CAIV-T, its use would be severely restricted should the timing of influenza vaccination coincide with a mass OPV immunisation campaign. Therefore, the purpose of this clinical trial is to investigate the effect, if any, of the co-administration of CAIV-T and OPV on the immune responses to the components of the vaccine, respectively.

Risks and Benefits

The frozen formulation of CAIV-T, manufactured by Aviron, Inc. has been evaluated in over 6,500 healthy children and 3,700 healthy adults. The results of completed pivotal studies are summarised in Table 1.

Table 1

Study	Population	Results

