An Investigator and/or Sponsor may withdraw a subject from the study if deemed appropriate. Criteria for termination of a subject from the study may include, but are not limited to, request for withdrawal, loss of subject to follow-up or clinically significant adverse events that constitute contraindications to further vaccine administration.

It is the policy of the sponsor, Wyeth Lederle Vaccines, that study data must be verifiable from the source data, which necessitates access to all original recordings, laboratory reports, and subjects' records. The investigator must therefore agree to allow access to subjects' records, and source data must be made available for all study data. The parent(s)/legal guardian(s) must also allow access to the subjects' medical records, and they will be informed of this and will be signing their agreement when giving informed consent. The subject diary card is considered to be a source document and relevant information regarding adverse events and concomitant medications from this document must be recorded onto the CRF.

The following selection criteria must be met in order for the subject to participate in the study.

Inclusion Criteria

Subject must fulfil all of the following conditions or characteristics in order to be considered for study enrolment and vaccination. Subjects must:

- be at least 6 months of age and less than 36 months of age at the time of first vaccination
- have received a full primary vaccination schedule consisting of three doses of OPV in the first year of life
- be in good health as determined by medical history, physical examination and clinical judgement
- have written informed consent of parent(s)/legal guardian(s) after the nature of the study has been explained
- along with their parent(s)/legal guardian(s) be available for duration of the trial (3 months)
- be reachable by study staff through home visit, clinic, or telephone for post-vaccination contacts.

Exclusion Criteria

Subjects with any of the following conditions or characteristics will be excluded from study enrolment:

- parent(s)/legal guardian(s) are perceived to be unavailable or difficult to contact for evaluation or study visits during the study period
- any serious chronic disease (e.g., with signs of cardiac or renal failure or severe malnutrition), including progressive neurological disease
- Down's syndrome or other known cytogenetic disorders

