Criteria for Temporarily Delaying Vaccination Administration

In general, the subject must be in good health (by physical examination and medical history) at the time of each study vaccination. The following conditions are temporary or self-limiting and a subject may receive study vaccine once the condition(s) has/have resolved and no other exclusion criteria are met:

- A febrile illness (axillary temperature > 37.5°C) or other acute illness within 36 hours prior to study vaccine administration.
- A respiratory illness in the subject and/or household member within 72 hours prior to study vaccine administration. Study vaccination of the subject may occur if a subject is experiencing mild symptoms of the common cold (e.g., slight cough and a runny nose), which is not going to be medically treated, and if the investigator feels that the subject's condition is not a respiratory illness and does not require any special clinical management. If the symptoms require medical intervention, it should be considered a respiratory illness and the study vaccination should be delayed until the illness has resolved. Vaccination should be delayed if a subject is taking medication (other than an antibiotic—see below) to prevent a particular respiratory related symptom (e.g., runny nose). In addition, if nasal blockage exists, it must be minimal enough to not reduce the likelihood of successful administration of the vaccine.
- Treatment of the subject with an antibiotic within 72 hours prior to study vaccine administration. Vaccination should be delayed if the subject requires any medical intervention with an antibiotic at the time of vaccination. If a subject is currently taking medicine (other than an antibiotic) at the time of vaccination for prophylaxis against a non-respiratory related illness, the subject may be vaccinated.
- Administration of any live virus vaccine (other than assigned study vaccine) within one month prior to enrolment or expected to receive another live virus vaccine (other than assigned study vaccine) within one month of vaccination in this study.
- Receipt of the third dose of the primary schedule of OPV within the 60 days prior to the first study vaccination.
- Receipt of any subsequent dose of OPV (a fourth or later dose) within 60 days prior to the first study vaccination.
- Receipt of a dose of any influenza treatment (commercial or investigational) in the two weeks prior to vaccination.

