The multidimensional comparison of primary interest is (1) to evaluate non-inferiority of the serum antibody response to OPV following concomitant administration with CAIV-T relative to the response to OPV administered separately temporally (at least 1 month apart) from CAIV-T and (2) to evaluate non-inferiority of the serum antibody response to CAIV-T following concomitant administration with OPV relative to the immune response of CAIV-T administered separately temporally (at least 1 month apart) from OPV. The response criterion for each viral strain of CAIV-T is a four-fold increase from baseline titre in the hemagglutination inhibition assay (HAI) for influenza virus strains A/H3N2, A/H1N1, and B. The response criterion for each antigen component of OPV is a post-vaccination titre of 1:10 for Poliovirus types 1, 2, and 3 by virus neutralisation assay. The primary analysis interval for influenza strains A/H1N1, A/H3N2, and B is one month following the second intranasal vaccination. The primary analysis interval for poliovirus types 1, 2, and 3 is one month following the single dose of OPV. The primary analysis endpoint will be achieved if lower limits of six independent 95% one-sided confidence intervals for differences in response rates are each greater than -10%.

It is expected that approximately 2,400 subjects will be enrolled in at multiple study sites. Determination of the appropriate sample for this study is dependent on the following assumptions:

-- Loss to follow-up is not greater than 15%.

-- Post-dose 2 influenza antibody response rates, measured as a four-fold or greater increase from baseline serum hemagglutination assay (HAI) will be similar to those observed in earlier studies of CAIV- T, ranging from 48% to 68% for the three strains □ Immune response rates for OPV measured at the end of the study by 1:10 or greater

virus neutralisation assay titres for Poliovirus types 1, 2, and 3 will be similar to those observed in earlier studies of OPV and may be as low as 75%.^{32,36}

-- The co-administration of CAIV-T with OPV will be demonstrated not to interfere with immune response to poliovirus and co-administration of OPV with CAIV-T will be demonstrated not to interfere with immune response to CAIV-T if each lower bound of 95% one-sided confidence intervals for the Poliovirus type 1, Poliovirus type 2, and

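### The primary polio response ignores the baseline titre in children already primed with three OPV doses, which pulls the comparison towards non-inferiority and probably leaves type 2 uninformative

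*Protocol*

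**What the plan says.** **Polio criterion.** The Data Analysis section says "The response criterion for each antigen component of OPV is a post-vaccination titre of 1:10 for Poliovirus types 1, 2, and 3", measured by neutralisation assay. The same section later repeats it as a titre of 1:10 or greater. Neither place refers to the pre-dose titre.

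**Influenza criterion.** By contrast, "The response criterion for each viral strain of CAIV-T is a four-fold increase from baseline titre". A seronegative-baseline population is also defined, but only for the influenza strains.

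**Who is enrolled.** Under Inclusion Criteria, children must "have received a full primary vaccination schedule consisting of three doses of OPV in the first year of life". Later doses are allowed too. The only limit is a delay, listed under the criteria for temporarily delaying vaccination: "Receipt of any subsequent dose of OPV (a fourth or later dose) within 60 days prior to the first study vaccination".

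**What three doses achieve.** The background section on OPV in developing countries gives median seroconversion percentages after three doses: "Poliovirus type 1 : 72", "Poliovirus type 2 : 95" and "Poliovirus types 3 : 65". The sample size assumptions say the polio rate after the study dose "may be as low as 75" per cent.

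**Decision rule.** Each of six differences must have a one-sided 95% lower limit above -10 points, and all six must succeed. A secondary analysis compares polio geometric mean titres, with a limit of 0.5 on the ratio. Blood is taken from every child before the first dose, and baseline antibody levels are to be reported.

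**The concern.** The second aim is to show that CAIV-T does not impair the immune response to the OPV dose given with it. The endpoint instead counts everyone at or above the threshold afterwards, including children who were there beforehand. Randomisation makes that carried-over share about equal in Groups 1 and 2, so it adds to both rates and cancels in the difference. Only children below 1:10 at entry can show interference. If they are few, even complete interference produces a small difference.

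In a non-inferiority trial this dilution favours the conclusion that the sponsor hopes to reach. The protocol avoids the problem for influenza by referring response to baseline, but not for polio, although the necessary serum is available.

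**Working it through.** **Inputs from the protocol.** Margin 10 points; one-sided level 0.05; 800 per group with 15% loss, so 800 × 0.85 = 680 evaluable; three-dose rates 72%, 95% and 65%; post-OPV rate as low as 75%.

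**Formula.** With true rates pT (Group 1) and pC (Group 2):
P(pass) = Φ[(0.10 − (pC − pT))/SE − 1.645], where SE = √[pT(1−pT)/680 + pC(1−pC)/680].

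**Plan's own figure.** At 55% v 55%, SE = √(2 × 0.2475/680) = 0.02698, and P = Φ(3.706 − 1.645) = 98.0%. This reproduces the stated 98%.

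**Model of total blocking (assumption).** Let b be the proportion at 1:10 or more on entry. The three-dose rates stand in for b, because the documents give no entry prevalence. Let s be the share of seronegatives that the study dose converts when OPV is given without CAIV-T. The documents do not give s, so a range is used. Under a complete block, Group 1 stays at b and Group 2 reaches b + (1−b)s. The deficit is (1−b)s.

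**Type 2.** At b = 95% the deficit cannot exceed 5 points. At the extreme, 95% v 100%, SE = √(0.0475/680) = 0.00836, and P = Φ(5.98 − 1.645) > 99.9%. A simulated score test gives 99.98%.

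**Types 1 and 3 at the planned 75%.**
- Type 1, 72% v 75%: SE = 0.0239, P = Φ(0.07/0.0239 − 1.645) = 90%.
- Type 3, 65% v 75%: the deficit equals the margin, so P = Φ(−1.645) = 5%.

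**Range of s** (Group 2 rate in brackets; the last column is the product, assuming independence):

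| s | Type 1 | Type 2 | Type 3 | All three |
|---|---|---|---|---|
| 10% | 91% (74.8%) | >99.9% | 82% (68.5%) | 75% |
| 20% | 59% (77.6%) | >99.9% | 33% (72.0%) | 19% |
| 25% | 36% (79.0%) | >99.9% | 13% (73.8%) | 5% |
| 28.6% | 22% (80.0%) | >99.9% | 5% (75.0%) | 1% |

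The deficit reaches 10 points at s = 0.10/0.28 = 36% for type 1 and 0.10/0.35 = 29% for type 3. For type 2 it would need 0.10/0.05 = 200%, which is impossible.

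**Sensitivity to the type 2 baseline, all seronegatives converting (s = 100%).** A total block passes 92% of the time at b = 93%, 61% at b = 92% and 5% at b = 90%.

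**The case against.** Four points can be made for the plan.

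1. **All six comparisons must succeed.** A reader might infer that the trial has no assay sensitivity for polio at all. The documents do not support that. With type 3 at 65% before and at least 75% after the study dose, a total block fails type 3 about 95% of the time, and with it the overall claim. The first three rows of the table put the type 3 reference below the plan's 75% floor. This stands, although the protection comes from one type's low three-dose rate and not from the endpoint's design.
2. **The 95% is a proxy.** A reader might also infer that type 2 is certain to pass. The figure is a median infant seroconversion rate from a review, not the prevalence of 1:10 or more at 6 to 36 months. This stands: certainty is lost if the entry rate is about 92% or lower and nearly all seronegatives convert. Permitted later doses would push the rate upwards, but no figure is given.
3. **The titre analysis is a safeguard.** The geometric mean titre ratio can register boosting in children already positive. This stands in part. The analysis is secondary and does not gate the claim.
4. **The hypothesis is worded in terms of antibody levels**, which a threshold fits. This has some force, but the second aim and the non-interference claim both concern responses.

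Further seronegative summaries may sit in an analysis plan not shown. The primary criterion, however, is fixed in the protocol.

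**Conclusion.** The defect is real. Prior immunity counts as response, and the bias is towards non-inferiority for all three polio types. Its size differs by type. If entry seropositivity is near 95%, the type 2 comparison is uninformative: complete blocking costs at most half the margin and passes more than 99.9% of the time. Type 1 is weak, with 90% passing at the planned 75%. Type 3 discriminates at 75%, with 5% passing, which is the nominal error rate. At trial level, a total block passes all three polio comparisons often only if the study dose converts few seronegatives: about 75%, 19% and 5% of the time at 10%, 20% and 25% conversion.

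These results rest on the three-dose rates as proxies for entry prevalence, 680 evaluable per group, titres that hold over the month, and independence between types for the joint figures.

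**What to change.** Define a baseline-referenced polio response for each type: from below 1:10 to 1:10 or more or, in children already at 1:10 or more, a four-fold rise. This parallels influenza. Make it the primary polio response. At minimum, pre-specify it as a key analysis with a 90% confidence interval that must be reported beside the threshold result before non-interference is claimed. Keep the proportion at 1:10 or more as the other analysis, and state that the type 2 threshold result is likely to be near ceiling.

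Report two further items descriptively, as evidence of assay sensitivity: Group 2 versus Group 3 (no OPV) at Visit 2, and the subset seronegative at baseline. Neither should be a gate. At a 95% baseline, Group 2 minus Group 3 could never reach 10 points for type 2. The type 2 subset would be about 680 × 0.05 = 34 per group, with power of about 21% at 50% v 50%; types 1 and 3 would have about 190 and 238.

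**Cost.** No extra visits or blood. If the new response is primary, worst-case power per test (true rate 50%) is 97.9%. Three influenza tests at 55% and three polio tests at 50% give 0.9804³ × 0.9795³ = 88.5%; six tests at the worst case give 88.3%. Polio at 75% under the present criterion gives 0.9804³ × 0.9955³ = 93%. The protocol's statement of at least 90% overall power must therefore be restated. If the combined response with OPV alone is below about 10%, the margin is again uninformative: at 6%, a total block (0% v 6%) still passes more than 99% of the time.

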Poliovirus type 3 response rates compared between Study Group 1 and Study Group 2 AND each lower bound of 95% one-sided confidence intervals for the A/H1N1, A/H3N2, and B response rates after 2 doses compared between Study Group 1 and Study Group 3 is greater than -10%. A study with at least 680 subjects completed in each treatment group would provide 98% power to demonstrate that a treatment with a true response rate of 55%, is non-inferior to a reference treatment with a true response rate of 55%, on a 10% criterion for non-inferiority. The simultaneous evaluation of six independent comparisons, each with 98% probability of success, provides an overall probability of success greater than 90%. The planned enrolment will provide at least 90% power to demonstrate non-inferiority of co-administration compared to separate administrations (at least one month apart) of liquid CAIV-T and OPV based on response criteria for antibody levels to three polio antigens and three influenza virus strains.

The proportion of responders for concomitant administration of CAIV-T and OPV

(Group 1) will be compared with the immune response to polio antigens in Group 2 and the immune response to influenza antigens in Group 3. The non-inferiority evaluation will be based on exact 90% two-sided confidence intervals for the six differences in proportions . If the lower limit of the confidence interval ** of $\frac{\text{co-admin}}{\text{reference}}$ is $\geq -10\%$ for polio antigen Types 1, 2, and 3 and for influenza strains A/H1N1, A/H3N2 and B, then the null hypothesis of inferiority with respect to a 10% criterion will be rejected at $\alpha=0.05$. StatXact will be used to determine the exact confidence interval. In a secondary analysis the comparison between co-administration and separate administration regimens will be based on the antibody titre (polio) or the titre ratio to baseline (influenza) expressed on a logarithmic scale. The t-test of the mean difference (in log) will be used to form the 90% confidence interval. The estimated difference and the confidence interval will then be exponentiated to obtain the GMT (geometric mean titre, polio) or GMR (geometric mean ratio, influenza) ratio (co-admin./reference) and its 90% confidence interval. If the lower limit of each confidence interval is ≥ 0.5 , the null hypothesis of inferiority with respect to a two-fold criterion will be rejected at $\alpha=0.05$.

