Each of the six immune responses will be evaluated at level of 0.05. The overall level for the six tests remains <0.05 as the null hypotheses for the six tests are required to be rejected simultaneously in order to demonstrate the acceptability of responses of co-administration.

Subjects who were immunised per protocol with blood samples drawn per protocol will be included in the immunogenicity analysis. Specifically, subjects must meet the following criteria to be included in the immunogenicity analysis:

-- The first blood draw (Pre Dose 1) must have occurred at the day of the first dose but prior to the first dose.

-- Time interval between the first and second doses must be 35 + 7 days.

- The second blood draw (Post Dose 1) must have occurred at the day of the second dose but prior to the second dose.
- Time interval between the second dose and the third blood draw (Post Dose 2) must be 35 + 7 days.

Influenza Seronegative Baseline Population – defined for each influenza strain: Those subjects of the immunogenicity evaluable population who had baseline titres for serum A/H1N1, A/H3N2, or B HAI less than or equal to 1:4.

Immunogenicity All Available Population: Subjects who received at least one dose of the assigned treatment and had a pre-dose and post-dose evaluation of serum antibodies.

Safety Population: Subjects who received at least one dose of the assigned treatment.

The demographic data, including gender, and age at each dose, of the immunogenicity and safety analysis populations will be summarised. Baseline serum antibody levels will be reported and the subject definition for seronegative baseline will be applied as a grouping criterion for some immunogenicity outcome summaries.

The primary measure of immunogenicity will be:

- Poliovirus types 1, 2, and 3 by virus neutralisation assay;
- Influenza virus strains A/H3N2, A/H1N1, and B by hemagglutination inhibition assay (HAI). OPV immune response for each poliovirus type is measured at the end of study by 1:10 or greater virus neutralisation assay titre.

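### The overall-power sentence is arithmetically wrong (0.98^6 is 88.6%, not above 90%), although the protocol's own response-rate assumptions can support the 90% conclusion

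*Protocol*

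**What the plan says.** The statements are all in the protocol's Data Analysis section.

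- **Success rule.** The primary objective is met if the "lower limits of six independent 95% one-sided confidence intervals for differences in response rates are each greater than -10" per cent. The section confirms that "the null hypotheses for the six tests are required to be rejected simultaneously".
- **Per-comparison power.** "A study with at least 680 subjects completed in each treatment group would provide 98% power" to show that "a treatment with a true response rate of 55%, is non-inferior to a reference treatment with a true response rate of 55" per cent, "on a 10% criterion for non-inferiority".
- **Overall power.** "The simultaneous evaluation of six independent comparisons, each with 98% probability of success, provides an overall probability of success greater than 90" per cent. The next sentence concludes: "The planned enrolment will provide at least 90% power to demonstrate non-inferiority of co-administration" over separate administration, for the three polio antigens and three influenza strains.
- **Assumptions listed beforehand.** "Loss to follow-up is not greater than 15" per cent; influenza response between 48% and 68% across the three strains; polio response possibly as low as 75%.

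The group table under Research Design and Methods gives 800 children per group.

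**The concern.** The sentence gives a number of comparisons, a probability for each and a dependence assumption, then a result that does not follow from them. It links the per-comparison calculation to the overall power claimed for enrolling 2,400 healthy children. Anyone checking that claim will start with this sentence and find it false.

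It also applies one power figure, derived for a 55% response rate, to all six comparisons. The section's own assumptions put polio response considerably higher. A reader therefore cannot tell which assumptions the 90% rests on.

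**Working it through.** **Inputs.** Per group: 800 randomised, of whom 15% are lost, so 800 × 0.85 = 680. Margin 0.10. One-sided alpha 0.05, z = 1.645. True difference zero. Response rates: 55% (the rate used for the 98%), 48% to 68% (influenza) and 75% (lowest polio rate).

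**Step 1: reproduce the 98%.** Power = Φ(margin/SE − 1.645), with SE = √(2p(1−p)/n).

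- At p = 0.55 and n = 680: SE = √(2 × 0.55 × 0.45/680) = 0.02698.
- 0.10/0.02698 − 1.645 = 2.06, and Φ(2.06) = 0.9804.

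The stated 98% is reproduced. Binomial enumeration gives 98.0% for a Wald test and 98.1% for a Farrington–Manning score test. A continuity-corrected normal calculation gives 97.8%.

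**Step 2: the overall figure from the sentence's own inputs.** Six independent comparisons, all required to succeed:

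- 0.98^6 = 0.8858, or 88.6%.
- With the unrounded 0.9804, the sixth power is 0.888, or 88.8%.
- To exceed 90%, each comparison needs more than 0.90^(1/6) = 0.9826.

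A power of 98.26% would also print as 98%, so rounding could in principle have explained the claim. It does not: the unrounded value is 98.04%, and no variant in Step 1 reaches 98.26%.

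Without independence, the sentence's inputs guarantee only the Bonferroni lower bound, 1 − 6 × 0.02 = 88.0%.

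**Step 3: the overall figure from the section's assumed response rates, 680 per group.**

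- Polio at 75%: SE = √(2 × 0.75 × 0.25/680) = 0.02348. Then 0.10/0.02348 − 1.645 = 2.61, and power is 0.9955 (99.55%, about 99.6%).
- Three influenza comparisons at 55% and three polio at 75%: 0.9804³ × 0.9955³ = 0.930.
- All three influenza strains at 48%, the low end of the range (0.9796 each), with polio at 75%: 92.8%.
- Influenza at 48%, 58% and 68% (58% is an assumed middle value), with polio at 75%: 93.9%.

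**Step 4: correlation.** The documents give no correlation between endpoints, so this step uses assumed values. A simulation with Group 1 shared across the comparisons and a common within-child correlation between responses gave:

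| Assumed correlation | All six at 55% | Polio 75%, influenza 55% |
|---|---|---|
| 0 | 88.7% | 93.0% |
| 0.1 | 89.0% | 93.0% |
| 0.3 | 89.7% | 93.4% |
| 0.5 | 90.7% | 94.0% |

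Positive correlation raises joint power, so the simple product is conservative in that case.

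**The case against.** The strongest defence is that the conclusion survives. The sentence on planned enrolment is true on the section's own listed rates: about 93% with polio at 75%, and 92.8% even with every influenza strain at 48%. The shortfall in the faulty sentence is only 1.4 points, smaller than many differences between power formulas. That stands as an argument about importance. It does not rescue the sentence, which sets an exact product of two stated numbers against a strict bound and assigns 98% to each of the six comparisons.

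A reader might infer three stronger points. The documents support none of them.

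- **That the trial is underpowered or needs more children.** Step 3 shows at least 90% on the stated rates with 680 per group.
- **That per-protocol exclusions use up the margin above 90%.** The immunogenicity analysis does require dosing and blood-draw windows to be met, and the 15% is described as loss to follow-up. But the documents give no rate for such exclusions. The 15% may also be generous: in the earlier South African trial described under Risks and Benefits, 1310 of 1394 children received a second dose, a loss of 84/1394 = 6.0%. That is another trial and covers second-dose receipt only, so it settles nothing either way.
- **That calling the comparisons independent overstates power.** Group 1 enters all six and several antigens are measured in the same children, so independence is doubtful. Positive correlation, however, raises the chance that all six succeed. Multiplying is then cautious, and this is no further error.

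**Conclusion.** Minor, but wrong as written. Six independent comparisons at 98% each give 88.6% (88.8% unrounded), not more than 90%. The conclusion of at least 90% power can still be supported, at about 93%, by using the assumed polio rate of 75% for the polio comparisons. The stated calculation does not do this.

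The 88.6% rests only on the sentence's own numbers and the rule that all six must succeed. The 93% rests on 680 evaluable children per group, no true difference between regimens, polio response of 75%, influenza response of 55%, and multiplication as if independent. Both use normal-approximation power. The Wald and score enumerations agree closely, but the exact interval planned in StatXact was not itself enumerated.

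**What to change.** Replace the sentence on the six comparisons with wording such as:

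> With 680 evaluable subjects per group, power is about 98% for each influenza comparison (55% response) and about 99.6% for each polio comparison (75% response). Multiplying these as if independent gives about 93% overall (about 89% if all six response rates were 55%). Positive correlation between endpoints would make these figures conservative.

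The following sentence, claiming at least 90% power, can stay, since it then follows from the rates given. The cost is a change of wording only. Enrolment, margin, alpha, tests and the decision rule are unaffected.
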